2.2 Endpoints

Primary outcome measures:

- The safety and tolerability of E-WE thrombin following administration of the active treatment will be evaluated versus pre-treatment and placebo by number and severity of AEs (including HD vascular access site reactions), physical examinations, bleeding time from the HD vascular access sites, vital sign measurements, 12-lead ECGs, clinical laboratory tests, and coagulation tests.

Secondary outcome measures:

- Pharmacodynamics of E-WE thrombin will be measured by APC-PCI and plasma APC-PCI will act as a surrogate marker for E-WE thrombin drug exposure.
- Efficacy of antithrombotic activity will be evaluated by thrombus accumulation within the dialyzer cartridge (evaluated by visual inspection) after E-WE thrombin active treatment versus pre-treatment and placebo.
- Efficiency of HD will be assessed using BUN levels before and after dialysis to determine urea removed by 4 hours of dialysis (Kt/V and URR) after E-WE thrombin active treatment versus pre-treatment and placebo.

Other outcome measures:

- Development of antibodies to E-WE thrombin or WT thrombin after drug exposure.

3. STUDY DESIGN

This is a phase 2, randomized, double-blind, placebo-controlled, single-dose study of E-WE thrombin designed to evaluate the safety and efficacy at 2 dose levels administered to patients with ESRD during HD conducted at one study centre in the US.

Patients will be enrolled in Cohort 1 or Cohort 2; cohorts will be dosed sequentially. Dosing of Cohort 2 will commence following completion of all study events for all patients in Cohort 1. Within each cohort, patients will be randomized to receive active drug or matching placebo as summarized below:

Table 1. Cohort and Treatment Randomization

Cohort	Treatment	Active:Placebo	Cohort Size
1	0.5 µg/kg bolus dose administered into the dialysis line immediately followed by a 0.25 µg/kg/hour continuous infusion dose into the dialysis line over 4 hours of E-WE thrombin or matching placebo, for a total dose of 1.5 µg/kg	2:1	12:6
2	1 µg/kg bolus dose administered into the dialysis line immediately followed by a 0.5 µg/kg/hour continuous infusion dose into the dialysis line over 4 hours of E-WE thrombin or matching placebo, for a total dose of 3 µg/kg	2:1	12:6

This study includes a screening period of 28 days prior to checking in to the CRU on Day -8. From Day -8 (8 days prior to dosing on Day 1) through Day 3, all patients will undergo HD five times and will be assessed for all scheduled procedures and endpoints before and after each HD session, using only one type of dialyzer cartridge for each patient.

On Day 1, prior to dosing, patients will undergo baseline measurements followed by initiation of a regular HD procedure, consistently using only one type of dialyzer cartridge for each patient. A single dose of E-WE thrombin or matching placebo will be administered into the dialysis line during the HD procedure. Patients will continue to undergo HD procedures and scheduled assessments from Day 1 through Day 3.

Study assessments will include AEs, including HD vascular access site (AV fistula or AV graft) reactions, physical examinations, vital sign measurements, 12-lead ECGs, clinical laboratory tests, coagulation tests, immunogenicity assessments, and PD blood sampling for APC-PCI and measurement of urea removed by 4 hours of dialysis to be performed throughout the study. On Days -7, -5, -2, 1, and 3, bleeding time from the HD vascular access sites on the AV fistula or AV graft (ladder or buttonhole technique) will be evaluated immediately at the end of the HD session. The dialyzer cartridge will be rinsed, visually inspected and graded against a standardized visual assessment scale at the end of the HD procedure, and photographed on 4 sides.

Additionally, plasma and dialysate samples will be collected and sent to Sponsor along with the used and rinsed dialyzer cartridges for potential internal evaluation of plasma protein C, dialysate urea, and total protein accumulation within the dialyzer cartridge.

All patients who receive the study drug or matching placebo (including patients who terminate the study early) will return to the CRU on Day 14 (\pm 2 days) for coagulation tests, immunogenicity sample collection, and to determine if any AE has occurred since the last study visit.

4. ANALYSIS POPULATIONS

4.1 Analysis Populations

Safety Population

All patients who received the study drug (active or matching placebo) will be included in the safety evaluations.

Pharmacodynamic Population

All patients who received the study drug (active or placebo) and had at least one postdose measurement of any of the PD assessment will be included in the PD evaluation.

4.2 Preliminary Data and Interim Analysis

Celerion has not been contracted to complete any interim safety and PD analyses.

5. TREATMENT DESCRIPTIONS

Patients will receive a total dose of either 1.5 $\mu\text{g}/\text{kg}$ E-WE thrombin, 3.0 $\mu\text{g}/\text{kg}$ E-WE thrombin, or matching placebo on Day 1.

Planned doses for each cohort of the study are as follows:

Cohort 1: Total dose of 1.5 $\mu\text{g}/\text{kg}$ E-WE thrombin or matching placebo on Day 1
Cohort 2: Total dose of 3.0 $\mu\text{g}/\text{kg}$ E-WE thrombin or matching placebo on Day 1

The patients' weight recorded at check-in will be used to calculate the study drug dose.

Treatments will be described as follows:

Cohort	Treatment	Short Description (used in text)	Long Description (used in Tables Figures and Listings)
Cohorts 1 & 2	P	Placebo (Pooled)	0.5/1.0 $\mu\text{g}/\text{kg}$ bolus dose of matching placebo followed by a 0.25/0.5 $\mu\text{g}/\text{kg}/\text{hour}$ continuous infusion over 4 hours for a total dose of 1.5/3.0 $\mu\text{g}/\text{kg}$ (Pooled matching placebo of Treatments A and B)
Cohort 1	A	1.5 $\mu\text{g}/\text{kg}$ E-WE thrombin	0.5 $\mu\text{g}/\text{kg}$ bolus dose of E-WE thrombin followed by a 0.25 $\mu\text{g}/\text{kg}/\text{hour}$ continuous infusion over 4 hours for a total dose of 1.5 $\mu\text{g}/\text{kg}$
Cohort 2	B	3.0 $\mu\text{g}/\text{kg}$ E-WE thrombin	1.0 $\mu\text{g}/\text{kg}$ bolus dose of E-WE thrombin followed by a 0.5 $\mu\text{g}/\text{kg}/\text{hour}$ continuous infusion over 4 hours for a total dose of 3.0 $\mu\text{g}/\text{kg}$

6. PHARMACODYNAMIC ANALYSIS

Plasma APC-PCI will be measured as a surrogate biomarker of drug exposure. APC-PCI will be used to detect the magnitude and duration of action of E-WE thrombin.

No pharmacokinetic (PK) or statistical analysis will be required for APC-PCI. Individual, mean, and median data for APC-PCI will be presented graphically for all treatments (2 active dose levels and pooled placebo).

6.1 Pharmacodynamic Assessment

Pharmacodynamic assessments will include evaluation of the efficacy of E-WE thrombin and the efficiency of HD.

6.1.1 Drug Efficacy

Efficacy of antithrombotic activity will be evaluated by thrombus accumulation within the dialyzer. Thrombus accumulation will be evaluated by visual inspection of the venous chamber and dialyzer membrane at the end of HD procedures and by a gradation using a standardized visual assessment scale. The dialyzer cartridge will be rinsed, visually inspected, graded, and photographed on 4 sides. The dialysis venous chamber will be visually inspected, graded and photographed. The number of dialyzer cartridges used for each HD session will be recorded.

Visual inspection of clotting in dialysis venous chamber will be recorded at the end of dialysis on Days -7, -5, -2, 1, and 3 with the following categories:

- 1 = No detectable clotting
- 2 = Presence of fibrinous ring or minimum clot affecting less than 5% of chamber space
- 3 = Clot formation (affecting more than 5% of but less than 25% of chamber space)
- 4 = Clot formation (affecting more than 25% of but less than 50% of chamber space)
- 5 = Clot formation (affecting more than 50% of but less than 75% of chamber space)
- 6 = Clot formation (affecting more than 75% of chamber space)
- 7 = Occluded (also assess the category of clot that caused occlusion)

Visual inspection of clotting in the dialysis filter will be recorded at the end of dialysis on Days -7, -5, -2, 1, and 3 with the following categories:

- 1 = No clotting, clean filter or few blood streaks (affecting less than 5% of the fibers seen at the surface of dialyzer),
- 2 = Blood streaks affecting more than 5% but less than 25 % of the fibers seen at the surface of the dialyzer,
- 3 = Blood streaks affecting more than 25% but less than 50 % of the fibers seen at the surface of the dialyzer,
- 4 = Blood streaks affecting more than 50% but less than 75 % of the fibers seen at the surface of the dialyzer,
- 5 = Blood streaks affecting more than 75% of the fibers seen at the surface if the dialyzer,
- 6 = Occluded (also assess the category of streaking at the time of occlusion)

Clotting categories will be listed and frequency summarized by Treatment and Day for all subjects in the Safety Population (2 active dose levels and pooled placebo).

Note: Plasma and dialysate samples will be frozen and sent to Sponsor along with the used and rinsed dialyzer cartridges and venous drip chambers for potential internal evaluation of plasma protein C, dialysate urea, and total protein accumulation within the dialyzer cartridge. Dialysate samples will be stored for up to 5 years following the last dosing for future analysis.

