9.2 Study Endpoints

Primary outcome measures:

- The safety and tolerability of E-WE thrombin following active treatment will be evaluated versus pre-treatment and placebo by number and severity of AEs (including HD vascular access site reactions), physical examinations, bleeding time from the HD vascular access sites, vital sign measurements, 12-lead ECGs, clinical laboratory tests, and coagulation tests.

Secondary outcome measures:

- PD of E-WE thrombin will be measured by APC-PCI and plasma APC-PCI will act as a surrogate marker for E-WE thrombin drug exposure.
- Efficacy of antithrombotic activity will be evaluated by thrombus accumulation within the dialyzer cartridge (evaluated by visual inspection) after E-WE thrombin active treatment versus pre-treatment and placebo.
- Efficiency of HD will be assessed using BUN levels before and after dialysis to determine urea removed by 4 hours of dialysis (Kt/V and URR) after E-WE thrombin active treatment versus pre-treatment and placebo.

Other outcome measures:

- Development of antibodies to E-WE thrombin or WT thrombin after drug exposure.

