13.6 Pharmacodynamic Assessments – Drug Efficacy and Efficiency of HD

Pharmacodynamic assessments will include evaluation of the efficacy of E-WE thrombin and the efficiency of HD. For all patients, PD assessments will be performed at scheduled time points as delineated in the Study Events Flow Chart ([Section 6](#)).

Efficacy of antithrombotic activity will be evaluated by thrombus accumulation:

- thrombus accumulation will be evaluated by visual inspection of the dialyzer membrane at the end of HD procedures and by a gradation using a standardized visual assessment scale [\[11\]](#). The dialyzer cartridge will be rinsed, visually inspected, graded, and photographed on 4 sides. The number of dialyzer cartridges used for each HD session will be recorded.

Efficiency of HD will be assessed by using BUN levels:

- BUN levels before and after dialysis will be used to determine urea removed by 4 hours of dialysis (Kt/V and URR) after E-WE thrombin active treatment versus pre-treatment and placebo.

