14.3.3 Pharmacodynamic Analyses

Placebo patients from Cohort 1 and Cohort 2 will be pooled for analysis.

Individual, mean, and median data for APC-PCI will be presented graphically for all treatments (2 active dose levels and pooled placebo).

Analysis will include assessments of drug efficacy and efficiency of HD. These will include changes in thrombus accumulation and measurement of urea removed by 4 hours of dialysis (Kt/V and URR).

The change from baseline in endpoints will be summarized by treatment (2 active dose levels and pooled placebo) and at each scheduled time point using descriptive statistics. The baseline values are any value observed from Day -8 to Day 1, prior to E-WE thrombin administration. An average of predose values may be used as baseline, as applicable. Any values after a single dose of E-WE thrombin are regarded as post-baseline values.

The change from baseline variables will be calculated as the post-baseline value minus the value at baseline.

Additional analyses may be performed as deemed necessary upon review of the data.

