8. SUMMARY OF CHANGES FROM PROTOCOL-PLANNED ANALYSIS

The analyses described in this SAP are aligned with those analyses described in the protocol.

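### The SAP adds an undeclared venous-chamber clotting scale, drops the protocol's change from baseline for clotting, URR and Kt/V, and plans no Day 1 estimate against placebo, yet states that it is aligned with the protocol.

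*SAP*

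**What the plan says.** **Endpoint.** Protocol 9.2 defines antithrombotic efficacy as "thrombus accumulation within the dialyzer cartridge (evaluated by visual inspection) after E-WE thrombin active treatment versus pre-treatment and placebo". Protocol 13.6 gives the method: "thrombus accumulation will be evaluated by visual inspection of the dialyzer membrane at the end of HD procedures". The venous chamber appears in neither section. SAP 2.2 repeats the cartridge endpoint and does not mention the chamber.

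**Assessment in the SAP.** SAP 6.1.1 states: "Thrombus accumulation will be evaluated by visual inspection of the venous chamber and dialyzer membrane at the end of HD procedures". It then sets out seven categories for the venous chamber and six for the dialysis filter, both graded on Days -7, -5, -2, 1 and 3.

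**Planned output.** For both scales the SAP says: "Clotting categories will be listed and frequency summarized by Treatment and Day for all subjects in the Safety Population". URR and Kt/V are summarized by treatment and day (SAP 6.1.2).

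**Baseline in the protocol.** The synopsis and Section 14.3.3 plan change from baseline for the PD endpoints by treatment, using descriptive statistics. Section 14.3.3 allows, but does not require, an average of predose values as the baseline.

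**Later analyses.** Protocol 14.3.3 adds: "Additional analyses may be performed as deemed necessary upon review of the data". SAP Section 1 treats analyses that it does not cover, or that the data prompt, as out of scope, and requires the study report to describe them.

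**Declared changes.** SAP Section 8 reads in full: "The analyses described in this SAP are aligned with those analyses described in the protocol".

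**The concern.** The efficacy question in Protocol 9.2 is comparative: "after E-WE thrombin active treatment versus pre-treatment and placebo". The planned tables show each arm on each day but never form that comparison. A reader who wants the size of the Day 1 effect has to construct it after the data are seen, choosing the scale, the baseline and the method at that point.

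The added chamber scale widens the choice. Nothing in 6.1.1 says that one scale carries the protocol endpoint and the other supports it.

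The run-in is also left unused for estimation. Three heparin-free sessions per patient measure each patient's own clotting tendency and dialysis efficiency before dosing. With 12 patients per arm, a raw Day 1 comparison carries any chance imbalance in those characteristics.

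Because Section 8 declares no departure, someone reading only the SAP would not learn that a scale was added or that a protocol analysis was left out.

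**Working it through.** **1. The two documents side by side**

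| Item | Protocol | SAP |
|---|---|---|
| Site graded | Dialyzer cartridge/membrane (9.2, 13.6) | Filter and venous chamber (6.1.1); endpoint text still cartridge only (2.2) |
| Change from baseline: clotting, URR, Kt/V | Planned (synopsis, 14.3.3) | Absent from 6.1.1, 6.1.2 and the table shells |
| Baseline | Predose values, average optional (14.3.3) | Not defined for these measures |
| Day 1 estimate against placebo | Endpoint defined that way (9.2); analysis descriptive | None |
| Declared changes | Not applicable | None (Section 8) |

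The SAP does keep change from baseline for chemistry and hematology, vital signs and ECG (7.4, 7.5, 7.7). The one difference it calculates for BUN is pre- minus post-dialysis within a session, which is not a change from baseline.

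**2. Sample size**

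Protocol 14.1 gives 36 patients: 2 × (12 + 6) = 36. Pooling placebo gives 12, 12 and 12. The number was chosen without statistical considerations, so there is no power figure to reproduce.

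**3. Precision with and without the run-in (illustration)**

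The inputs are 12 versus 12 and three run-in sessions. The within-patient correlation r is assumed equal between any two sessions. The documents give no value, so a range is shown.

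- Unadjusted half-width of the 95% CI: t(22) × √(2/12) = 2.074 × 0.408 = 0.85 SD.
- Variance factor for ANCOVA on the mean of three sessions: f = 1 − 3r²/(1 + 2r).
- Variance factor for simple change from that mean: g = (4/3)(1 − r).

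| r | f | Half-width, ANCOVA (0.847 × √f) | g | Half-width, change (0.847 × √g) |
|---|---|---|---|---|
| 0.3 | 0.831 | 0.77 SD | 0.933 | 0.82 SD |
| 0.5 | 0.625 | 0.67 SD | 0.667 | 0.69 SD |
| 0.7 | 0.388 | 0.53 SD | 0.400 | 0.54 SD |

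This applies directly to URR and Kt/V. For the ordinal filter grade it is only a guide.

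**4. If the comparisons were tested (illustration)**

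The plan contains no test, so the 5% level is an assumption. Two scales by two doses make four comparisons. Both doses share one pooled placebo group, so for a given scale the two dose contrasts correlate at (1/12)/(2/12) = 0.5. In a simulation of 100,000 null trials with normal group means, at least one of the four passed two-sided 5% in:

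| Correlation between scales | Any of four | Two scales, one dose |
|---|---|---|
| 0 | 17.2% | 9.7% |
| 0.3 | 16.8% | 9.4% |
| 0.5 | 16.1% | 9.0% |
| 0.8 | 14.1% | 7.9% |

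**The case against.** The strongest defence is that the efficacy analysis is deliberately descriptive. Safety is the primary objective, the sample size has no statistical basis, and no hypothesis test is planned. Both scales are tabulated for every arm and session, so a run-in imbalance would be visible. Protocol 14.3 lets the SAP modify the plan, and it requires an amendment only for major changes to the primary endpoints or their analysis. All of this stands. It excuses the absence of a powered test. It does not make the Section 8 statement correct, and it gives no reason to omit a summary that the protocol promised.

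Four stronger readings are tempting, and the documents do not support them:

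- **That the efficacy conclusion will come from data-driven analyses.** Protocol 14.3.3 only permits further analyses, and SAP Section 1 puts them out of scope and makes them reportable. What can be said is that any effect estimate would be post hoc.
- **That the chamber scale has displaced the filter, because its table comes first.** Table order is not precedence, and SAP 2.2 still names the cartridge. The gap is that 6.1.1 does not make the link.
- **That occluded sessions will be counted twice.** The SAP asks for a second category to be assessed when occlusion occurs. It does not say that both enter the frequency table. It leaves the rule unstated, as it does when a second filter or chamber is used.
- **That four looks carry an 18.5% false-positive chance.** That is 1 − 0.95⁴, which needs independent comparisons. The shared placebo rules this out.

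The precision gain also depends on an assumed correlation. At 0.3 it is modest.

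**Conclusion.** The point holds as a gap in specification and a wrong statement of alignment. The chamber scale is an addition, change from baseline for clotting, URR and Kt/V is an omission, and Section 8 declares neither. The endpoint's comparison with placebo has no planned Day 1 estimate. The omission concerns a secondary objective and does not affect the safety analysis.

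Using the run-in mean would narrow a 12 versus 12 interval from 0.85 SD to between 0.77 and 0.53 SD, for assumed correlations of 0.3 to 0.7. If two scales by two doses were each tested at 5%, the chance of at least one false positive would be about 14% to 17%. That figure describes a hypothetical use of the tables and not an analysis in the plan. The change should be made before unblinding, because after that the same estimate can no longer count as pre-specified.

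**What to change.** 1. **SAP 6.1.1:** name the Day 1 dialyzer-filter grade as the protocol's efficacy measure, and label the venous-chamber grade as added by the SAP and supportive.
2. **SAP 6.1.1 and 6.1.2:** fix the baseline as the patient's mean over Days -7, -5 and -2, and restore change from baseline for clotting, URR and Kt/V.
3. **Estimate:** for each dose against pooled placebo, pre-specify one baseline-adjusted Day 1 estimate with a 95% CI. Use rank ANCOVA or proportional odds for the filter grade, with the choice made in advance, and ANCOVA for URR and Kt/V. Present these as estimation and not as a powered test.
4. **Counting rule:** state that each session enters the frequency table once, report occlusion separately, and say which grade is used when a session is occluded or needs a second filter or chamber.
5. **SAP Section 8:** list the added scale and the added estimate, and remove the unqualified alignment statement.

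The cost is SAP wording, revised shells and a few lines of code. All the data are already collected at the five scheduled sessions. Under Protocol 14.3 a change to a secondary analysis does not call for a protocol amendment.

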6.1.2 Efficiency of HD

Efficiency of HD will be assessed by using blood urea nitrogen (BUN) levels before and after dialysis to determine urea removed by 4 hours of dialysis (Kt/V and URR) after E-WE thrombin active treatment versus pre-treatment and placebo.

BUN: Samples for BUN will be collected pre- and post-dialysis on Days -7, -5, -2, 1, and 3.

The change in BUN values on Days -7, -5, -2, 1, and 3 will be calculated by subtracting the post-dialysis BUN from the pre-dialysis BUN values for each day separately. BUN values will be listed and summarized by treatment and Day in tables and figures for all subjects in the PD Population (2 active dose levels and pooled placebo).

URR and Kt/V: The derived PD parameters urea reduction ratio (URR) and Kt/V will be calculated from the pre- and post-dialysis BUN values on Days -7, -5, -2, 1, and 3.

URR will be calculated using the following formula:

$$\text{URR} = (1 - (\text{post-dialysis BUN} / \text{pre-dialysis BUN})) * 100$$

Kt/V will be calculated using the following formula:

$$sp \frac{Kt}{V} = -\ln(R - (0.008 \times t)) + (4 - (3.5 \times R)) \times \frac{UF}{Wt}$$

Where R = BUN Post-dialysis/BUN Pre-dialysis

t = Time of HD

UF = Pre-dialysis patient weight – Post-dialysis patient weight

Wt = Post-dialysis weight of patient.

URR and Kt/V values will be listed and summarized by treatment and Day in tables for all subjects in the PD Population (2 active dose levels and pooled placebo).

6.1.3 Internal Analysis by the Sponsor:

The following analyses may be performed by the Sponsor for internal purposes; these results may be included in the appendices of the CSR.

- Protein C Analysis
- Dialysate Analysis
- Analysis of Protein Accumulation Within the Dialyzer Cartridge

Full details are located in the protocol.

6.2 Measurements and Collection Schedule

APC-PCI: For all patients, blood samples for the determination of APC-PCI will be collected on Day 1 at predose (hour 0, at least 1 hour prior the start of HD session) and at 0.167, 0.5, 1, 2, 4, 6, and 24 hours after E-WE thrombin bolus dose.

All APC-PCI concentration data will be included in the individual concentration-time plots (based on actual sample times), and in the mean concentration-time plots (based on nominal sample times). However, if there are any significant deviations from nominal sample times, some concentration data may be excluded from mean concentration-time plots and/or additional concentration-time plots of the mean data may be provided. All deviations and excluded data will be provided and discussed in the CSR.

Protein C: For all patients, blood samples for the determination of protein C will be collected at the start and end of dialysis on Days -7, -5, -2 and 3. On Day 1, samples will be collected at predose (hour 0, at least 1 hour prior the start of HD session) and at 0.167, 0.5, 1, 2, 4, 6, and 24 hours after E-WE thrombin bolus dose.

